13.4.3 Supportive Analyses of the Primary Endpoint

As a supportive analyses, the risk of treatment failure over the entire 48 week period of Stage 2 will be summarized using Kaplan-Meier product limit estimates, and a stratified log-rank test will be conducted with complete follow-up of participants. Additional covariates including participant and disease characteristics at study entry and in Stage 1 treatment withdrawal, and time-dependent covariates during Stage 2 will be explored in a multivariable Cox models

using main effects and interaction terms. Multivariable models will be fully defined in the statistical analysis plan (SAP). Finally, in addition to considering heterogeneity from immunologically defined subsets and other observed factors, a supportive analysis will explore the use of frailty models to consider variability from additional unobserved factors using random effects terms.

13.4.4 Analyses of Secondary Safety Endpoints

Safety analyses will be performed on the safety sample and will be assessed by summarizing AEs separately for each stage of the study. The length of time participants are followed within each stage is variable and could depend on if a participant meets treatment failure. To account for potential differential duration of study participation, AE summaries by treatment group will include the number of events per person-year in addition to the number and percentage of events and participants experiencing events. AEs and SAEs will be summarized by system organ class, preferred term, and severity grade.

Safety endpoints identified in Section 3.3.2 Safety Endpoints, will be summarized and listed separately for each stage of the study. For each such endpoint, the number of events per person-year as well as numbers and percentages of events and participants who experience these events will be summarized overall in Stage 1 and by treatment group in Stage 2 and 3. No formal statistical testing will be performed to compare safety between treatment groups.

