5.2 Risks of voclosporin as cited in the Investigator Brochure and Package Insert

Risks cited below are noted in the voclosporin Investigator's Brochure [65] and Package Insert [21].

Contraindications:

- Voclosporin is contraindicated in patients with hypersensitivity or anaphylactic reactions to voclosporin or any constituents [65].
- Voclosporin should not be given with strong CYP3A4 inhibitors (e.g., ketoconazole, itraconazole, clarithromycin). Voclosporin exposure was 18-fold higher in the presence of the strong CYP3A4 inhibitor (ketoconazole) compared to voclosporin administered alone [65].
- Voclosporin should not be given in patients with hypertensive urgency or BP > 165/105 mmHg [21].
- Voclosporin is not recommended for patients with a baseline eGFR < 45 mL/min per 1.73 m² unless benefit exceeds risks [21].

Hypertension: Voclosporin can cause or worsen systemic HTN. Mild or moderate HTN is encountered more frequently than severe HTN. Serious adverse drug reactions (SADR) classified by the MedDRA preferred term "hypertension" are considered "expected" for the purpose of regulatory reporting. Life-threatening or fatal SADRs are "unexpected". HTN may require antihypertensive therapy.

Decreases in GFR: Voclosporin can cause chronic and/or acute nephrotoxicity. eGFR should be monitored regularly and dose adjustments considered for decreases in eGFR. In the first 4 weeks of treatment with voclosporin, hemodynamic reductions in eGFR have been observed, which subsequently stabilize. Chronic nephrotoxicity has been observed at levels of CNI suppression needed in organ transplantation. The level of CNI suppression of voclosporin in LN is lower than that generally required in transplantation induction and maintenance. Renal impairment and acute kidney injury occurred more frequently in voclosporin-treated patients than placebo-treated patients.

Serious Infections: Immunosuppressants, including voclosporin, may increase the risk of developing bacterial, viral, fungal, and protozoal infections, including opportunistic infections. These infections may be serious and have fatal outcomes. Serious infections are listed as a boxed warning in the package insert [21].

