In addition, a simulation study was conducted to determine the power for the supportive analysis using log-rank tests for time until treatment failure under assumptions of non-constant and non-proportional hazards based on the results of previous studies using BOLD designs in lupus populations [22, 93, 94]. Specifically, under an assumption the baseline hazard doubles at Week 12 with an attenuation of long-acting corticosteroids, a proportional hazard corresponding to an increase in survival at Stage 2 Week 24 from 15% to 35% with MMF (HR = 0.55) results in 80.0% power. When all treatment benefit from MMF is restricted to after Week 12, power of the log-rank test decreases to 61.3%, but there remains power to detect larger treatment effects (power = 87.9% when SMMF,24 = 45% and SPlacebo,24 = 15%).

The baseline immunologic cluster would be a useful marker for identifying individuals with a propensity to respond to MMF if some clusters have a very poor response and others have a large response. Hence, the by-cluster comparisons are powered to identify clusters with an MMF response of 60-80% survival at Stage 2 Week 24, which is well above that expected for the overall population.

Table 13.1 gives the number required per arm in a given cluster to achieve 80% power to detect large differences in survival over 24 weeks between arms (based on log-rank test, $\alpha=0.1$, 2-sided). For example, if the underlying placebo survival is 10% at 24 weeks, then 6-9 per arm within a given cluster gives 80% power to detect survival in the MMF arm ranging from 60-80%. Power for within-cluster comparisons will be maximized if numbers per arm are equal. Although stratifying randomization by baseline cluster assignment (7 clusters) is not feasible, stratification by gene expression signature (3 levels) serves as a first-cut approximation to the cluster assignment and should facilitate balance between arms.

Table 13.1. Cluster comparisons: # per arm to achieve 80% power on comparison of survival over 24 weeks

		*Survival at Stage 2 Week 24: MMF				
		60%	65%	70%	75%	80%
*Survival at Stage 2 Week 24: Placebo	5%	7	6	6	5	5
	10%	9	8	7	6	6
	15%	13	11	9	8	7

* Assumed underlying %survival in the population of MMF (or placebo) -treated patients.

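### The only exposure-adjusted safety measure is a person-year rate pooled over a whole stage, which compares arms fairly only if adverse-event risk is constant over time

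*Combined protocol and SAP*

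**What the plan says.** Section 13.4.4 plans safety by "summarizing AEs separately for each stage of the study". It states the difficulty openly: "The length of time participants are followed within each stage is variable and could depend on if a participant meets treatment failure". Its remedy is the rate: "To account for potential differential duration of study participation, AE summaries by treatment group will include the number of events per person-year". The same sentence continues "in addition to the number and percentage of events and participants experiencing events". For the four endpoints of Section 3.3.2 the set is the same: "the number of events per person-year as well as numbers and percentages of events and participants who experience these events will be summarized". Only Stages 2 and 3 are split by arm; Stage 1 is shown as a single group. No formal safety test is planned. The section gives no time windows within a stage and no time-to-first-event summary for adverse events. It does not say which summary to read when the rate and the percentage disagree.

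Three other places bear on this:
- Section 3.1.2: a participant who fails by Week 24, and for whom an injection suffices, goes straight to Stage 3. Those who have not failed stay on Stage 2 medication to Week 48.
- Section 5.2, on voclosporin: "In the first 4 weeks of treatment with voclosporin, hemodynamic reductions in eGFR have been observed, which subsequently stabilize".
- Section 13.7 models the failure hazard "under an assumption the baseline hazard doubles at Week 12 with an attenuation of long-acting corticosteroids".

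**The concern.** Dividing events by person-time puts two arms on the same footing when risk per week is the same throughout. If risk is concentrated early, the extra weeks in the better arm enter the denominator and add few events to the numerator. The drug's rate then falls because it works, not because it is safer. The percentage of participants with an event has the opposite weakness: when risk continues, the arm followed longer has more opportunity for events.

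The secondary objective in Section 2.3 is to describe safety for MMF, MMF plus voclosporin and placebo. With no formal testing, these by-arm tables are the between-arm safety evidence. Which column can be trusted depends on when the events occur, and whole-stage tables do not show that.

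**Working it through.** **1. The plan's own figures reproduce, so its survival inputs can be used.** With 60 per arm, exact enumeration of the two-sided unpooled Z-test at 15% versus 35% gives 73.8% power (stated 74%). At 15% versus 37% it gives 80.7% (stated at least 80%). The hazard ratio is ln(0.35)/ln(0.15) = 0.553 (stated 0.55). Events are 60×0.85 + 60×0.65 = 90, for which the Schoenfeld formula gives 80.1% power (the plan's simulation: 80.0%).

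**2. Mean time in Stage 2.** From Section 13.7, the hazard is λ to Week 12 and 2λ afterwards, so the cumulative hazard to Week 24 is 12λ + 24λ = 36λ and λ = −ln(S24)/36. Assumptions added here: 2λ continues to Week 48, every failure leaves the stage, and adverse events are independent of failure.

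Mean time E = (1 − S12)/λ + (S12 − S48)/(2λ):
- Placebo, S24 = 15%: λ = 0.0527, S12 = 0.531, S48 = 0.012. E = 8.89 + 4.93 = 13.8 weeks.
- MMF, S24 = 35%: λ = 0.0292, S12 = 0.705, S48 = 0.086. E = 10.13 + 10.60 = 20.7 weeks.
- MMF, S24 = 50%: λ = 0.0193, S12 = 0.794, S48 = 0.198. E = 10.71 + 15.46 = 26.2 weeks.

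For 60 per arm, 13.8 and 20.7 weeks are 15.9 and 23.8 person-years, a ratio of 1.50.

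**3. What the pooled rate shows for early events.** Adverse-event timing is an assumption; the documents give no such hazards. Let A(w) = (1 − e^(−λw))/λ be the mean time at risk in Weeks 0 to w, for w up to 12. If all events fall in that window with equal weekly risk, the whole-stage rate ratio is [A_MMF(w)/E_MMF] / [A_P(w)/E_P].
- Weeks 0-4, 35%: (3.78/20.73)/(3.61/13.82) = 0.70.
- Weeks 0-4, 50%: (3.85/26.17)/(3.61/13.82) = 0.56.
- Weeks 0-12, 35%: (10.13/20.73)/(8.89/13.82) = 0.76.

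A true ratio of 1.5 in Weeks 0-4 would show as 1.5×0.698 = 1.05 at 35%, or 1.5×0.564 = 0.85 at 50%.

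**4. What the percentages show.** With weekly event hazard a, the chance of a first event in Weeks 0 to w before exit is a(1 − e^(−(λ+a)w))/(λ+a). For Weeks 0-4 with a 4-week risk of about 20%, this gives 18.1% versus 18.9%. The other rows use a = 0.02 per week and integrate over the stated period.

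| Timing of risk (equal true risk, 15% vs 35%) | Pooled rate ratio | Percentage ratio |
|---|---|---|
| Weeks 0-4 | 0.70 | 1.05 |
| Weeks 0-12 | 0.76 | 1.13 |
| Days 31-180 | 0.96 | 1.40 |
| Constant to Week 48 | 1.00 | 1.39 |

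At a = 0.01 the last row's percentages are 12.5% versus 17.9%, ratio 1.44.

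**5. Sensitivity of the 0.70.**
- If 20% of failures stay to Week 24 (Section 3.1.2 keeps in follow-up those who need other lupus medication), and with or without a 4-week safety visit for those who have not failed by Week 24, the range is 0.68 to 0.75.
- If all MMF benefit comes after Week 12, mean MMF time is 19.8 weeks and the ratio is 13.82/19.80 = 0.70.
- If person-time is cut at Week 24, it is (3.78/16.21)/(3.61/12.51) = 0.81.

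**6. The proposed measure.** In a Weeks 0-4 window, expected events are a×A(4) and time at risk is A(4), so the rate is a in each arm. The ratio is then 1.00 when risks are equal and 1.50 when the true ratio is 1.5, provided that risk is roughly constant within the window.

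**The case against.** A reader who stops at the person-year clause might infer that safety is given only as rates, so that a real early excess would vanish from the output. The documents do not support that. The same sentence adds numbers and percentages. For Weeks 0-4 those are nearly unbiased: 1.05 when the truth is 1.00, and 16.4% versus 24.5% (1.50) when the true ratio is 1.5. Nor is it right that neither planned summary ever compares like with like: the percentage does nearly so for the earliest events, and the rate does so for constant risk.

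A reader might also take Section 13.7 as saying that adverse-event risk changes over time. The doubling there is of the failure hazard. The direct statement of an early effect that then stabilises concerns voclosporin, hence Stage 3, whereas the figures above are for Stage 2. The Section 5.1 remark on MMF neutropenia at days 31 to 180 comes from transplant patients, and for that period the pooled rate is nearly right (0.96).

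The safety comparison is descriptive, so no test or decision rule is affected. Sections 13.4.3 and 13.4.6 defer other details to an SAP, which could add safety tables, although 13.4.4 itself defers nothing.

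All of this stands and narrows the point. It does not remove it: for risk over Weeks 0-12 both summaries are wrong and point in opposite directions, and nothing planned tells the reader which case applies.

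**Conclusion.** The point holds in limited form. The plan's one correction for failure-dependent follow-up is a whole-stage rate that is valid only under constant risk. At the plan's 15% versus 35%, it would understate MMF's relative rate of Weeks 0-4 events by about 30% (0.70; 0.68 to 0.75 if some failures stay to Week 24), and by about 44% at 50% MMF survival (0.56). Ratios of 13.8/20.7 = 0.67 and 13.8/26.2 = 0.53 are limits for events at the very start of the stage and should not be quoted as expected values.

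These sizes rest on assumed event timing, independence of events and failure, and the failure hazard continuing past Week 24. The size in Stage 3 cannot be computed, because no survival figure is stated for the combination arm; treatment there also stops at 24 weeks, so the long tail of Stage 2 is absent. This is an inexpensive improvement to descriptive reporting, not a fault in the trial's inference.

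**What to change.** In Section 13.4.4, for the four Section 3.3.2 endpoints and the AE and SAE totals:
- Add by-arm event rates in a few windows since the start of the stage, for example Weeks 0-4, 4-12 and 12-24, plus 24-48 in Stage 2.
- Optionally add the cumulative incidence of first event at Weeks 4, 12 and 24.
- State that these are the basis for the descriptive between-arm reading. Keep the whole-stage rate and the percentages beside them.

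The cost is wording and a few tables from data already collected. The downside is sparse counts and wide intervals in later windows: at the plan's rates about 60×0.15 = 9 placebo and 60×0.35 = 21 MMF participants remain failure-free at Week 24, and Section 13.7 expects Stage 3 cells of about 18 to 24. Any cumulative incidence needs a caveat that stage exit may be informative, because failure under Section 3.5.1 includes flare and permanent discontinuation for any reason, toxicity among them.

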13.4.5 Analyses of Secondary Efficacy Endpoints

The key secondary efficacy endpoint is clinical response at Stage 2 Week 24, defined by the BICLA (see Section 3.3.1, Efficacy Endpoints). A Fisher's exact test (2-sided $\alpha=0.05$) will be performed to test the hypothesis that there is no difference in the proportion of responders between treatment groups. This analysis will also be repeated at Stage 3 Week 24. An additional supportive Stage 3 analysis will use the most recent assessment before the Stage 3 Day 0 visit as the reference (see Section 3.5.3, BILAG-based Combined Lupus Assessment (BICLA)).

For Stage 3, the cumulative incidence of participants who experience a treatment failure in Stage 3 will be evaluated. The primary analysis will be repeated considering treatment failures occurring during the time period from Stage 3 re-randomization through Stage 3 Week 24.

Time to treatment failure will also be evaluated in Stage 3, where the Kaplan-Meier estimation and log-rank tests from the supportive analysis of the primary analysis will be repeated for the time period from Stage 3 re-randomization through Stage 3 Week 24.

Given the unknown samples sizes and subgroups defined by Stage 2 treatment assignment, all inferential analyses for Stage 3 are considered supportive; p-values for test of differences among groups will be presented without adjustment for multiple comparisons, and p-values of < 0.10 will be considered notable findings.

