3.1.2 Stage 2: Randomization

One hundred and twenty qualifying participants who withdraw from treatment as described in protocol Section 3.1.1, *Stage 1: Treatment Withdrawal*, and meet improvement criteria for randomization as outlined in Section 4.2.2, *Inclusion criteria required prior to randomization*, will be randomized (1:1) to receive up to 48 weeks of either MMF or corresponding MMF placebo. For the first 2 weeks, a scheduled “taper-up” of MMF will take place. Participants will receive 500 mg MMF (or corresponding MMF placebo) BID for 7 days, followed by 500mg and 1,000mg MMF (or corresponding MMF placebo) in divided doses for 7 days. They will then continue at a stable dose of 1,000mg MMF (or corresponding MMF placebo) BID. Visits to evaluate AEs, vital signs, hematology and chemistry, study medication compliance, medication use, disease status, participant reported outcomes, and to obtain biomarker samples will occur every 4 weeks after randomization.

Participants will be followed for a maximum of 48 weeks on study-provided medication in Stage 2. If a participant experiences an increase in SLE symptoms at any scheduled or unscheduled visit at or before the Stage 2 Week 24 visit, they will proceed in the study as follows:

- If the participant is deemed a Stage 2 treatment failure as defined in protocol Section 3.2, *Primary Endpoint*, and a corticosteroid injection is deemed sufficient for treatment without new or increased lupus medication, then a blood sample for mechanistic studies will be drawn, the injection will be administered, and the participant will immediately proceed to Stage 3: Re-randomization. (See Section 3.1.3, *Stage 3 Re-Randomization*).
- If the participant is deemed a Stage 2 treatment failure as defined in protocol Section 3.2, *Primary Endpoint*, and a corticosteroid injection is deemed sufficient for treatment without new or increased lupus medication, but the participant refuses the corticosteroid injection, then a blood sample for mechanistic studies will be drawn, and the participant will still immediately proceed to Stage 3: Re-randomization without the corticosteroid injection. (See Section 3.1.3, *Stage 3: Re-Randomization*).

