3.5 Definitions

3.5.1 Treatment Failure

Treatment failure is defined as the first occurrence after randomization (Stage 2) or as the first occurrence after re-randomization (Stage 3) of any of the following events:

- Corticosteroid injections or treatment with a new or increased lupus medication, except the occasional use of corticosteroids for reasons not associated with SLE flare (see Section 7.1.2.2, *Prednisone (or equivalent)* for additional information); or
- BILAG flare, defined as any item marked new or worse that could support a BILAG A (severe flare) or 2 organs with items marked new or worse that could support a BILAG B (moderate flare), and if the participant's condition is deemed by the investigator to be "moderately worse" or "much worse" compared to the day of randomization, as assessed by the CGI-C; or
- Premature permanent discontinuation of study-assigned treatment for any reason.

For Stage 2, the reference values for the CGI-C should be the investigator's determination of the participant's condition at the Stage 2 Day 0 Randomization Visit. For Stage 3, the reference values for the CGI-C should be the investigator's determination of the participant's condition at the most recent assessment before the Stage 3 Re-randomization Visit.

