3.5.3 BILAG-based Combined Lupus Assessment (BICLA)

Clinical response at Week 24, defined by the BICLA [71] as follows:

- All BILAG A scores must improve to B, C, or D, and
- All BILAG B scores must improve to C or D, and
- No new BILAG A scores among organs scored as B, C, D, or E, and
- ≤ 1 new BILAG B scores among organs scored as C, D, or E, and
- No worsening of H-SLEDAI total score, and
- Less than a 10% increase (worsening) in the Physician's Global Assessment (visual analogue scale).

For Stage 2 and Stage 3, the reference values for BILAG, H-SLEDAI total score and PGA are the assessments obtained at the Screening Visit. For Stage 3, additional supportive analyses will use the most recent assessment before the Stage 3 Re-Randomization Visit as the reference value for H-SLEDAI total score, BILAG scores, and PGA.

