4.2 Inclusion Criteria

4.2.1 Inclusion Criteria

Participants must meet all of the following criteria to be eligible for randomization as study participants.

1. Aged ≥ 18 and ≤ 60 years at the time of informed consent.
2. Meets EULAR/ACR 2019 criteria for SLE [3].
3. Moderately severe, active, but non-organ threatening disease. Specifically, signs or symptoms meeting criteria for a minimum of:
 - a. 1 BILAG A (severe) score in the constitutional, musculoskeletal or mucocutaneous system at the time of screening. See Section 4.3, *Exclusion Criteria* number 2 for additional detail.
 - b. 2 BILAG B (moderate) activity scores in any organ systems; or
 - c. 1 BILAG B (moderate) activity score in any organ systems **and** a SELENA-SLEDAI score of ≥ 6 .
 - If there is only 1 BILAG B score:
 - If a musculoskeletal BILAG B is scored due to moderate arthritis, where some loss off functional range of movements was present on several days over the last 4 weeks, there must also be a minimum of at least 3 joints that are both tender and

swollen due to lupus disease activity in wrists, MCPs or PIPs for the participant to qualify.

- If a mucocutaneous BILAG B is scored due to acute or subacute cutaneous skin eruption, the rash must cover at least 4% of the body surface area for the participant to qualify. Any active discoid lesion or other form of chronic cutaneous lupus would be qualifying.

4. Approval, by an adjudication committee of a brief entry packet describing the type, severity and duration of symptoms meeting the minimal criteria for entry. The participant will meet this criterion if the committee is confident of all of the following:
 - a. Convincing diagnosis of SLE,
 - b. Active disease, due to SLE, warranting the potential of dual therapy with potent immune modulators,
 - c. No medical or other condition to contraindicate participation in a placebo-controlled, outpatient study of this design.
5. Women of childbearing potential must have a negative serum pregnancy test at screening.
6. Able or willing to use reliable methods of contraception, as outlined in the Mycophenolate REMS brochure for health care providers, from 4 weeks prior to first randomization to 6 weeks after completion of the study. This criterion applies to females of reproductive potential. Mycophenolate REMS Program acceptable contraceptive methods are outlined in Appendix 1, see Section 19.1.

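### The BICLA key secondary endpoint has no rule for treatment failures: some could count as responders, and most would have no Stage 2 Week 24 value although the analysis sets keep them

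*Combined protocol and SAP*

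**What the plan says.** Section 13.4.5 names the endpoint ("The key secondary efficacy endpoint is clinical response at Stage 2 Week 24, defined by the BICLA") and tests it with Fisher's exact test at two-sided 0.05. Section 3.5.3 lists six criteria: four on BILAG, one on H-SLEDAI and one on PGA. The first is "All BILAG A scores must improve to B, C, or D, and". For the comparison, "the reference values for BILAG, H-SLEDAI total score and PGA are the assessments obtained at the Screening Visit". No criterion concerns rescue, treatment failure or stopping study drug.

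Treatment failure (3.5.1) has three routes: a corticosteroid injection or new or increased lupus medication; a BILAG flare with investigator-rated worsening; or "Premature permanent discontinuation of study-assigned treatment for any reason". The global rating of change is made against the "condition at the Stage 2 Day 0 Randomization Visit", that is, after the steroid response, whereas BICLA looks back to active disease at Screening.

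What happens after failure depends on the route:

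- If an injection is judged sufficient, "the injection will be administered, and the participant will immediately proceed to Stage 3: Re-randomization" (3.1.2). A participant who refuses the injection also moves on.
- If new or increased lupus medication is needed, the participant is barred from Stage 3 but is followed to Stage 2 Week 24, or to about four weeks after the last dose if later (3.1.2). Table 8.1, footnote P, has those who exit at Week 24 complete the end-of-study assessments then.
- Participants who stop study drug for intolerance or an adverse reaction may stay in the study (6.5, 11.1).

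Section 13.4.1.1 uses mITT for every Stage 2 efficacy analysis. PP1, which also serves the Week 24 secondary endpoints, expressly admits participants who failed by Week 24.

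**The concern.** The definition is silent about the event that most participants are expected to have, and this creates two separate problems.

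First, misclassification. A rescued failure assessed at Week 24 on non-study medication can satisfy all six criteria and be credited as a responder to the randomized arm. Section 1.2.2 says a flaring participant becomes a non-responder for that part of the study, and 13.7 forecasts responders as those who have not failed. Neither statement is a BICLA rule.

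Second, missing values. Participants who enter Stage 3 before Week 24 leave the Stage 2 schedule, so no Stage 2 Week 24 BICLA exists for them. The analysis sets keep them and no value is assigned. Because the gap is caused by failure itself and is larger on placebo, omitting these participants would not be neutral.

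**Working it through.** **Inputs.** From 13.7: 60 per arm; planning failure-free rates at Week 24 of 10-15% (placebo) and 35-50% (MMF); Stage 3 entry forecast of at least 48 of 60 placebo (80%) and approximately 36 of 60 MMF (60%). I add 20 vs 40%, which is what the entry forecast implies if every failure moves.

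**Plan's figures reproduced.** 0.80 × 60 + 0.60 × 60 = 48 + 36 = 84, and 84/120 = 70%. The plan's pooled primary power also reproduces: 73.8% by exact enumeration at 15 vs 35%, against 74% stated.

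**Failures never re-randomized.** At 15 vs 35%, failures are 51 + 39 = 90, and 90 − 84 = 6 (3 per arm). At 20 vs 40%, 48 + 36 − 84 = 0. At 10 vs 35%, 54 + 39 − 84 = 9, but only if placebo entry stays at its stated floor of 48. These are differences between planning figures, not forecasts in the plan.

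**Failures without a Week 24 value.** A failure declared at the Week 24 visit has an assessment, so it must be removed from the 84. I assume that failures arising in weeks 20-24 are declared at that visit. With failure-free rate S at Week 24, S(20) = S^(20/24) for a constant hazard, or S^(28/36) if the hazard doubles at Week 12 (the assumption in 13.7's log-rank simulation). The late share is (S(20) − S)/(1 − S). For S = 15%, constant hazard: (0.206 − 0.150)/0.850 = 6.6%. Movers are capped at the number of failures, so at 50% MMF survival only 30 can move, not 36.

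| Placebo vs MMF failure-free | Movers | No value: constant hazard | No value: doubling hazard |
|---|---|---|---|
| 15 vs 35% | 48 + 36 | 44.9 + 32.3 = 77.1 | 43.6 + 30.9 = 74.5 |
| 20 vs 40% | 48 + 36 | 44.3 + 32.0 = 76.3 | 42.8 + 30.6 = 73.4 |
| 10 vs 35% | 48 + 36 | 45.5 + 32.3 = 77.8 | 44.4 + 30.9 = 75.3 |
| 10 vs 50% | 48 + 30 | 45.5 + 26.3 = 71.8 | 44.4 + 25.0 = 69.4 |
| 15 vs 50% | 48 + 30 | 44.9 + 26.3 = 71.2 | 43.6 + 25.0 = 68.6 |

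The range is about 69-78 of 120 (57-65%): 43-46 on placebo and 25-32 on MMF. The remaining 6-11 movers are declared at Week 24 and do have a value.

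**Can a failure meet BICLA?** Rescue, injection and discontinuation failures have no disease-activity threshold, so yes. For a flare failure at Week 24 the room is limited but real. Entry allows "1 BILAG A (severe) score in the constitutional, musculoskeletal or mucocutaneous system at the time of screening", and an organ that was A at Screening and is B at Week 24 counts as improved. Two such organs pass, and so does one such organ plus one new B, because 3.5.3 tolerates one new B. Any A that has not improved, any new A, any unimproved B, or two new Bs blocks response.

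**Effect of the choice.** Illustration at 15 vs 35%, assuming all failure-free participants (9 placebo, 21 MMF) are BICLA responders:

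- Every failure a non-responder: 9/60 vs 21/60, Fisher p=0.019.
- All 84 Stage 3 entrants omitted: denominators 60 − 48 = 12 and 60 − 36 = 24, so 9/12 vs 21/24, p=0.38. Only the 3 never-re-randomized failures per arm remain as non-responders.
- Only movers without a value omitted, with late-declared failures kept as non-responders: 9/15 vs 21/28, p=0.32 (constant hazard); 9/16 vs 21/29, p=0.33 (doubling).
- No omissions, but the 3 never-re-randomized failures per arm scored as responders: 12/60 vs 24/60, p=0.028. If only placebo's 3 are so scored: 12/60 vs 21/60, p=0.10.

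**The case against.** The best defence is that the intent is plain. Section 1.2.2 calls a flaring participant a non-responder, 13.7 equates response with not having failed, and a separate SAP is mentioned in which a derivation rule could sit. I have not seen that SAP, so I cannot say the rule exists nowhere. But the deferrals to it cover multivariable models (13.4.3) and exploratory clinical endpoints (13.4.6); 13.4.5 defers nothing. Section 13.4.6 also defines Stage 3 response by BICLA alone, while 13.7 counts responders as those who have not failed, so two definitions are in use.

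A second defence has more force. mITT analyses participants regardless of compliance, and scoring the observed Week 24 BICLA of someone who stopped study drug for intolerance, without rescue, fits that wording. Sections 1.2.1 and 1.2.2 speak of waning steroid response and flare, not intolerance. Statisticians may differ here, which is why that analysis belongs among the supportive ones.

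Third, many flare failures cannot meet BICLA. That is true, and it keeps the misclassification route small.

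Stage 3 carries lower stakes: 13.4.5 calls its inference supportive and 13.7 calls it exploratory.

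**Conclusion.** The gap is real and should be fixed. As written, a rescued failure or one first declared at Week 24 can be a responder. The first group is probably small, 0 to about 6 participants never re-randomized; the documents give no count for either group. The larger problem is the 69-78 of 120 participants (57-65%) with no Stage 2 Week 24 BICLA and no stated value, more of them on placebo. That range rests on the Stage 3 entry forecast, the two hazard shapes, declaration of weeks 20-24 failures at the Week 24 visit, and movers capped at failures. The p-values illustrate one assumed pattern and do not predict a result.

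A reader might infer more than the documents support:

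- That 84 is a maximum, or a share of 120 failures. It is a forecast (a floor for placebo, an approximation for MMF) out of 120 randomized participants.
- That all 84 lack a value. Those declared at the Week 24 visit have one.
- That the sponsor plans to drop the unscored participants. The text does not say so; it says nothing.
- That BICLA is underpowered. The plan claims no power for it, and any figure needs a BICLA response rate that the documents do not give.
- That the primary analysis is compromised. It uses treatment failure directly and is unaffected.

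**What to change.** Add one derivation rule to 3.5.3 and 13.4.5, and carry it into the SAP: a participant who meets treatment failure (3.5.1) at or before the Week 24 assessment, including a failure declared at that visit, or whose Week 24 BICLA is missing, is a BICLA non-responder in the mITT analysis. Apply the failure part in PP1 as well. Use the same rule for Stage 3 Week 24 in mITT3, so that 13.4.6 and the 13.7 forecast share one definition of non-responder.

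Report two supportive analyses: observed cases only, and one that uses the observed Week 24 BICLA of participants who stopped study drug for intolerance without rescue.

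The cost is a short text change and no new data. Reported response rates will be lower than under a more permissive rule. BICLA response becomes a subset of failure-free status, so it adds less information independent of the primary endpoint.
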